#### An Adverse Drug Reaction is considered serious if it:

- Results in Death
- Is life threatening
- Requires additional inpatient hospitalization or prolongation of existing hospitalization
- Results in persistent or significant disability / incapacity
- Results in a congenital anomaly or birth defect

• Other medically significant event that requires immediate medical or surgical intervention

#### Unexpected is defined as:

• Not consistent with Investigators Brochure or SmPC

#### Causal Relationship is defined as:

- There are facts/evidence to suggest a causal relationship
- As judged by the reporting health care professional to have reasonable suspected causal relationship

Medical judgement should be exercised in deciding whether an Adverse Event / Reaction is serious in other situations. Important Adverse Events / Reactions that are not immediately life-threatening or do not result in death or hospitalisation but may jeopardise the patient or may require intervention to prevent one of the other outcomes listed in the definition above, should also be considered serious.

**Death:** is the outcome of an Adverse Event. The event to be reported comprehensively is the medical condition leading to death, e.g. underlying disease, accident.

**Life-threatening:** in the definition of a Serious Adverse Event or Adverse Reaction refers to an event in which the patient was at risk of death at the time of the event; it does not refer to an event which hypothetically might have caused death if it was more severe.

#### 10.3. Suspected Expected Serious Adverse Reaction (SESAR)

Any adverse reaction that is classed in nature as serious and which is consistent with the available information on the medicinal product in question set out in the SmPC

#### 10.4. Suspected Unexpected Serious Adverse Reaction (SUSAR)

Any adverse reaction that is classed in nature as serious and which is not consistent with the available information on the medicinal product in question set out in the SmPC.

#### 10.5. Recording of Adverse Events

All adverse events occurring after the start of the study must be reported, according to previously provided definitions, whether they are considered serious or not and regardless of the relationship to teh strudy medication will be documented in the CRF and were applicable reported. Subject entry into the study is defined as the time the informed consent is signed.

The nature of each individual AE, date and time of onset, duration, severity, relationship, any actions taken as well as outcome must be documented by the investigator. Additionally, it will be recorded whether the AE was serious nor not. Details of change to the dosing schedule or any corrective treatment must be recorded on the appropriate pages of the CRF.

The investigator is obliged to follow-up patients with AEs until the event has subsided, the condition is considered medically stable, or the patient is no longer available to follow-up. Patients who discontinue the study drug due to adverse experiences (clinical or laboratory) will be treated and followed according to established acceptable medical practice - all pertinent information concerning the outcome of such treatment will be entered on the CRF. AEs already documented in the CRF at a previous visit and designated as continuing must be reviewed at each visit. If an AE is resolved, documentation in the CRF must be completed to that effect. If an AE changes in frequency or severity during a study period, a NEW record of that experience will be initiated.

#### 10.5.1. Definition of Adverse Event intensity

Intensity	Definition
Mild	Patient is aware of signs and symptoms, but they are easily tolerated
Moderate	Signs / symptoms cause sufficient discomfort to interfere with usual activities
Severe	Patient is incapable to work or perform usual activities

#### **10.5.2.** Definition of Adverse Event causality

On the basis of the WHO-UMC system for standardised case causality assessment (www.who-umc.org), the following categories are used to describe the degree of causality (all points should be complied with):

#### Definite

- Event or laboratory test abnormality, with plausible time relationship to drug intake
- Cannot be explained by disease or other drugs
- Response to withdrawal plausible (pharmacologically, pathologically)
- Event definitive pharmacologically or phenomenologically (i.e. an objective and specific medical disorder or a recognised pharmacological phenomenon)
- Re-challenge satisfactory, if necessary

#### Probable

• Event or laboratory test abnormality, with reasonable time relationship to drug intake

- Unlikely to be attributed to disease or other drugs
- Response to withdrawal clinically reasonable (for details refer to WHO-UMC)
- Re-challenge not required

#### Possible

- Event or laboratory test abnormality, with reasonable time relationship to drug intake
- Could also be explained by disease or other drugs
- Information on drug withdrawal may be lacking or unclear

#### Unlikely

- Event or laboratory test abnormality, with a time to drug intake that makes a relationship improbable (but not impossible)
- Disease or other drugs provide plausible explanations

#### Not related

• The event does not follow a reasonable temporal sequence from administration of the IMP and is clearly related to other factors, such as clinical state, therapeutic intervention or concomitant therapy

#### Not assessable

- Report suggesting an adverse reaction
- Cannot be judged because information is insufficient or contradictory
- Data cannot be supplemented or verified

All cases judged by any or both assessors as having a "reasonable causal relationship" to the IMP qualify as ADR. This corresponds to the categories "definite", "probable" and "possible".

#### 10.6. Reporting of Serious Adverse Events

All Serious Adverse Reactions and all Unexpected Serious/Adverse Reactions with at least a suspicion of causal relationship to the investigational product must be reported to the Coordinator within 24 hours (one working day) of the Investigator becoming first knowledge. Preference in the reporting is the SAE report by e-mail to [contact].

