#### 10.2. Adverse Drug Reaction (ADR)

All untoward and unintended responses to an Investigational Product related to any application / dose administered. The phrase "responses to an Investigational Product" means having a reasonable causal relationship as judged by either the Investigator or the Coordinator. The expression reasonable means to convey in general that there is evidence or argument to suggest a causal relationship.

Regarding marketed Investigational Products: a response to a product which is noxious and unintended and which occurs at applications normally used in man for prophylaxis, diagnosis, or therapy of diseases or for modification of physiological function.

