#### 10.2.1. Serious Adverse Event or Serious Adverse Reaction (SAE/SAR)

Serious Adverse Events will due to the underlying constitution of the patient be considered for AE documentation. Serious Adverse Drug Reactions will be dealt with as described below. Expedited Reporting is required if the following criteria apply (ICH E2A):

- Serious
- Unexpected
- Reasonable causal relationship to study treatment

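### The 24-hour report covers only suspected reactions, so the Coordinator gets no prompt look at serious events the site rates unrelated; the time limit itself is stated two ways

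*Protocol*

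**What the plan says.** The protocol gives the causality judgement to two parties. Section 10.2 defines a reaction as a response "having a reasonable causal relationship as judged by either the Investigator or the Coordinator". Section 10.5.2 repeats the principle at the end of its causality categories ("All cases judged by any or both assessors as having a" reasonable causal relationship are reactions), and counts definite, probable and possible as meeting it.

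The prompt-reporting duty is in section 10.6. Despite a heading about serious adverse events, it applies to "All Serious Adverse Reactions and all Unexpected Serious/Adverse Reactions with at least a suspicion of causal relationship to the investigational product". These "must be reported to the Coordinator within 24 hours (one working day) of the Investigator becoming first knowledge".

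For serious events not classed as reactions, section 10.2.1 says: "Serious Adverse Events will due to the underlying constitution of the patient be considered for AE documentation". It then adds: "Serious Adverse Drug Reactions will be dealt with as described below". Its definition of causality for expedited reporting rests on the site: "As judged by the reporting health care professional to have reasonable suspected causal relationship".

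Section 10.5 requires all adverse events, serious or not and related or not, to be documented in the CRF and reported where that applies. It gives no time limit.

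**The concern.** A rule that either of two assessors may call an event a reaction is useful mainly when they disagree, and above all when the site says unrelated and the Coordinator would say otherwise. That requires the Coordinator to see events the site does not suspect. Section 10.6 filters on suspicion before the report is sent, so those are the events with no prompt route to the second assessor.

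This matters more than usual here. Section 13.11.1 anticipates deaths during the study, and a blinded investigator may readily put a death or a recurrent stroke down to the underlying disease. The study-level discontinuation criteria in section 6.6.1 name only recruitment and protocol violations, and the protocol describes no interim safety review. Individual case reporting is therefore the main route it sets out for prompt safety oversight.

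The time limit raises a second, smaller issue. It equates 24 hours with one working day, while sections 7.1.1 and 11.1 schedule infusions on ten consecutive days.

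**Working it through.** No sample size, power or event rate is involved and the protocol gives no figure to reproduce. The check follows a serious event from the site to the Coordinator, by the site's causality category (section 10.5.2).

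**Route by category**

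| Site's rating | Counts as a reaction on the site's view? | 24-hour report under 10.6? | Otherwise |
|---|---|---|---|
| Definite, probable, possible | Yes | Yes | – |
| Unlikely, not related | No | No | CRF record (10.5), adverse event documentation (10.2.1) |
| Not assessable | Not stated | Unclear | Same, if not reported |

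The second row is where a Coordinator's differing opinion could turn an event into a reaction, and it is the row with no deadline.

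**Can 10.6 be read to include the Coordinator's view?** Section 10.2 makes an event a reaction if the Coordinator judges it so, so one could argue that 10.6 already covers it. That is circular: the report runs from Investigator to Coordinator and the clock starts with the Investigator's knowledge, so the Coordinator's view cannot trigger a report the Coordinator has not received. Section 10.2.1 points the same way by relying on the reporting professional's judgement.

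**Other routes to the Coordinator**
- Section 15.2: monitoring visits at regular intervals, frequency not given.
- Section 15.6: centralised statistical monitoring as ongoing surveillance, with no timeline for serious events.
- Section 6.7.3: the Study Safety Officer is to be informed when the code is broken, which does not cover serious events in general.
- Section 16.7.1: signed CRFs available within two weeks after each patient completes. This is the only fixed limit.

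**Size of the backstop delay**
- Inputs: cycle 1 on days 1 to 10; final visit on day 360; two weeks = 14 days.
- Latest CRF availability: 360 + 14 = day 374.
- Event on day 1: 374 − 1 = 373 days.
- Event on day 10: 374 − 10 = 364 days.

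These are nominal dates, before the visit window of ±3 working days. They are upper limits, since monitoring may find the event sooner.

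**The two clocks**
- Any run of ten consecutive days contains a full weekend, so every treatment cycle given as scheduled is affected.
- Site learns of an event on Friday evening. Limit of 24 hours: Saturday evening.
- Limit of one working day, read as the next working day: Monday, up to about 3 × 24 = 72 hours if Monday evening is the end point.

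**The case against.** The strongest reply is that sections 10.2 and 10.5.2 are classification rules with no time limit. The Coordinator can apply them whenever the data arrive, from CRFs, monitoring visits or centralised monitoring. This stands. A reader might infer that the either-assessor rule cannot work at all; the protocol does not support that, and the gap is one of timing.

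Second, the trigger is low. An event with a reasonable time relationship to the drug is rated possible even if the stroke could also explain it, and possible counts as a reaction. This also stands. A reader might infer that anything the site attributes to the stroke escapes prompt reporting, but the gap is limited to events rated unlikely or not related, with not assessable left open.

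Third, section 10.5 begins with a duty to report all adverse events regardless of relationship. The sentence is garbled and ends by requiring reporting only where applicable. It names no recipient and no deadline, so it does not close the gap, but it is a reason to reconcile the sections. Section 10.2.1 likewise says that serious events will be considered for documentation, which is looser than confining them to it. The slash wording in 10.6 may even extend the duty to unexpected non-serious reactions.

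Fourth, this is a phase IV study of a marketed product, and section 10.2.1 gives a reason for the selective route: the patients' underlying condition. That explains a wish to limit reports. It does not explain naming a second assessor who is not promptly shown the cases on which a second view could matter.

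**Conclusion.** The concern holds as a timing gap. For serious events the site rates unlikely or not related, and perhaps not assessable, the protocol names a second causality assessor but guarantees that assessor no sight of the event within the expedited window. The only fixed limit is two weeks after the patient completes, up to 373 days after an event on day 1, assuming nominal visit dates and no earlier discovery through monitoring. The 24-hour limit is separately ambiguous; the 72-hour figure assumes that one working day means the next working day.

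Two stronger conclusions are tempting and should not be drawn. One is that most serious events after stroke fall into the gap: the protocol gives no event rate and no split by causality category, so the share is unknown. The other is that prompt reporting would by itself expose an excess on the drug: that is a comparison between arms, which single blinded case reports do not make. Nothing here touches the primary efficacy analysis. It should still be corrected, because the sections disagree on safety oversight and the remedy is cheap.

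**What to change.** 1. In section 10.6, require all serious adverse events, whatever the Investigator's causality view, to be sent to the Coordinator within 24 clock hours of the Investigator becoming aware. Delete the working-day parenthesis.
2. Reconcile section 10.2.1 (the sentence on documenting serious events, and the reliance on the reporting professional's judgement) and section 10.5 (the unclear reporting duty) with the either-assessor rule in 10.2 and 10.5.2.
3. In the same revision, state how not-assessable events are handled and whether unexpected non-serious reactions fall under 10.6.

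The cost is a wording amendment and more serious-event reports for the site to send and the Coordinator to process. Patients undergo no additional procedures, and neither treatment nor the analysis changes.

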#### 10.7. Adverse Event/Reaction follow-up procedures

Adverse Events/ Reactions will be followed up throughout the course of the clinical study and any changes will be recorded in the CRF.

#### 11. STUDY SCHEDULE

#### 11.1. **Procedures at Each Visit**

#### Visit 1 – Screening PART 1 - within 72h after onset of the stroke (Study Day -30)

Visit 1 will be perfomed 30  $\pm$  3 working days prior to randomization and the baseline assessment

- In/exclusion criteria PART 1
  - CT
  - NIH Stroke Scale score between 5-15 at inpatient admission
  - IQ Code
- Demographic data
- Medical history
- Concomittant Medication

#### Run-In Period – Study Day -30 to Study Day 1

The Run-In period shall continue for 25 to 30 days beginning visit one. During the Run-In period the following will be performed

- MRI will be performed before study baseline
- Monitoring of concomitant medication
- Standard stroke treatment

#### Visit 2 – Screening PART 2 & Baseline Assessment – Study Day 1

- Informed Consent (signed up to Visit 2 start)
- In/exclusion criteria PART 2
  - Mini-Mental State Examination (MMSE)
  - Goodglass & Kaplan Score
- Randomization
- Primary Evaluation Scales Baseline Assessment
  - Stroop Color Word test (Stroop)
  - Trail-Making-Test Part A (TMT-A)
  - Digit Span Backward Task (DS-BW)
  - Digit Symbol (DS-WPSI)
  - Verbal Fluency Test CFL Version (VFT-CFL)
  - Rey Auditory Verbal Learning Test (RAVLT)
- Secondary Evaluation Scales Baseline Assessment
  - Montreal Cognitive Assessment (MOCA)

- Modified Rankin Scale
- NIH Stroke Score
- Hospital Anxiety and Depression Scale
- EQ-5D-5L
- Drug Safety Parameters
  - Adverse Events
- Concomittant Medication Monitoring

#### Treatment Cycle 1 – Study Day 1 to 10

During the first treatment cycle each patient shall receive 10 infusions, once daily on 10 consecutive days. The first infusion will be given after all baseline assessments have been performed. The following procedures will be performed during treatment visits:

- Adverse Event Monitoring
- Concomittant Medication Monitoring

## Treatment Cycle 2 – Study Day 61 to 70

During the second treatment cycle each patient shall receive 10 infusions, once daily on 10 consecutive days. The following procedures will be performed during treatment visits:

- Adverse Event Monitoring
- Concomittant Medication Monitoring

#### Treatment Cycle 3 – Study Day 121 to 130

During the second treatment cycle each patient shall receive 10 infusions, once daily on 10 consecutive days. The last infusion will be given on the day of Visit 3 before the assessments The following procedures will be performed during treatment visits:

- Adverse Event Monitoring
- Concomittant Medication Monitoring

#### Visit 3 – Efficacy & Safety Assessment – Study Day 180

- Primary Evaluation Scales Baseline Assessment
  - Stroop Color Word test (Stroop)
  - Trail-Making-Test Part A (TMT-A)
  - Digit Span Backward Task (DS-BW)
  - Digit Symbol (DS-WPSI)
  - Verbal Fluency Test CFL Version (VFT-CFL)
  - Rey Auditory Verbal Learning Test (RAVLT)

- Secondary Evaluation Scales Baseline Assessment
  - Montreal Cognitive Assessment (MOCA)
  - Modified Rankin Scale
  - NIH Stroke Score
  - Hospital Anxiety and Depression Scale
  - EQ-5D-5L
- Drug Safety Parameters
  - Adverse Events
- Concomittant Medication Monitoring

#### Treatment Cycle 4 – Study Day 241 to 250

During the second treatment cycle each patient shall receive 10 infusions, once daily on 10 consecutive days. The following procedures will be performed during treatment visits:

- Adverse Event Monitoring
- Concomittant Medication Monitoring

#### Visit 4 – Efficacy & Safety Assessment – Study Day 360

- Primary Evaluation Scales Baseline Assessment
  - Stroop Color Word test (Stroop)
  - Trail-Making-Test Part A (TMT-A)
  - Digit Span Backward Task (DS-BW)
  - Digit Symbol (DS-WPSI)
  - Verbal Fluency Test CFL Version (VFT-CFL)
  - Rey Auditory Verbal Learning Test (RAVLT)
- Secondary Evaluation Scales Baseline Assessment
  - Montreal Cognitive Assessment (MOCA)
  - Modified Rankin Scale
  - NIH Stroke Score
  - Hospital Anxiety and Depression Scale
  - EQ-5D-5L
- Drug Safety Parameters
  - Adverse Events
- Concomittant Medication Monitoring

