#### 5. STUDY DESIGN

Randomized, double-blind study design

One dose group (Cerebrolysin 30ml) shall be tested against placebo. The two study groups are therefore:

Study Group 1:	30ml Cerebrolysin
Study Group 2:	Placebo (0.9% NaCl)

The trial will be conducted in subjects suffering from ischemic stroke in the anterior circulation, either TACS or PACS. The diagnosis of the ischemic stroke as well as the location of the stroke will be determined clinically and confirmed by neuroimaging.

The study extends over an observation period of 390 days. Five visits for clinical evaluation are planned for the following points in time:

**Visit 1 (Study Day -30±3 working days) – Screening Part 1** is scheduled within 72h after the onset of stroke and is followed by a  $30 \pm 3$  working days run-in period for the patients. **Visit 2 - Screening Part 2 & Baseline Evaluation** is scheduled at study day 1. Following to the baseline assessment, study participants shall begin with Treatment Course 1 comprising ten once daily infusions of study medication on study days 1 to 10. Following a treatment free period of one month, patients shall receive Treatment Course 2 comprising ten once daily infusions of study medication on study days 61-70 and again after a break of one months Treatment Course 3 on study days 121-130. **Visit 3 – Efficacy & Safety Evaluation** which is scheduled for study day 180. The final **Visit 4 – Efficacy & Safety Evaluation** which is the primary endpoint of the study is scheduled for study day 360 post stroke. All treatment cycles and efficacy evaluations will be performed within a window of ±3 working days.

The study shall be initiated in May 2020. The first patient at each participating center should be enrolled within 2 months of initiation. The duration of the study is expected to be 4 years.

Clinical Study Phase: Phase IV

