#### Placebo

250 ml of 0.9% saline solution

The study medication will be infused over a period of 30 to 45 minutes. The study drug will be administered once daily by IV infusion for ten consecutive days starting on the day of the baseline examination. The first administration of study medication will be administered after all baseline assessment have been completed.

This treatment will be repeated with ten daily IV infusions on study days 1-10, 61-70, 121-130, and 241-250. Infusions will be given at approximately the same time on each day.

If a patient misses an infusion, it may be added at the end of each treatment course.

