#### 11.2. Assessment of Compliance

Compliance will be documented by recording the date and time of the administration in the CRF. The number of IV infusions actually administered to each patient will be calculated as the percentage of the total number of IV infusions planned per protocol and will provide a measure of treatment compliance. All treatment cycles and efficacy

evaluations will be performed within a window of  $\pm 3$  working days.

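### Section 11.1 puts the last cycle 3 infusion both on day 130 and on the day of Visit 3 (day 180), so what the first confirmatory test measures is left open

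*Protocol*

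**What the plan says.** **Cycle 3 and Visit 3.** Section 11.1 heads the cycle "Treatment Cycle 3 – Study Day 121 to 130" and states that "each patient shall receive 10 infusions, once daily on 10 consecutive days". It then says: "The last infusion will be given on the day of Visit 3 before the assessments". The next visit heading is "Visit 3 – Efficacy & Safety Assessment – Study Day 180". The synopsis and section 5 also place Visit 3 on day 180.

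**Tolerances.** Section 5 says "All treatment cycles and efficacy evaluations will be performed within a window of ±3 working days", and section 11.2 repeats this. Section 7.1.1 lets a missed infusion be made up at the end of its course.

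**Number of courses.** Section 7.1.1 gives "ten daily IV infusions on study days 1-10, 61-70, 121-130, and 241-250". The synopsis and section 11.1 also list a fourth cycle on days 241 to 250. Section 5 describes courses 1 and 2, then "again after a break of one months Treatment Course 3 on study days 121-130", and goes straight on to Visits 3 and 4 without a fourth course.

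**Use in the analysis.** Section 13.7 tests change from baseline to day 180 first and change to day 360 second. Section 11.2 defines compliance from the infusions given, "calculated as the percentage of the total number of IV infusions planned per protocol". Section 13.14 removes patients below 80% from the per-protocol set, which sections 13.9 and 13.12.4 give the same scientific weight as the full analysis set.

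**The concern.** The paragraph on cycle 3 cannot be carried out as written. Either the cycle ends on day 130 or its last infusion is given on the day of the Visit 3 tests. The contradiction sits in the visit-procedures section, which is the part that staff work from.

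The day-180 assessment supplies the first test in the fixed sequence, and day 360 can be confirmatory only if day 180 succeeds. A difference between arms measured shortly after an infusion on the same day is not the same quantity as one measured 50 days after the last infusion. The protocol should fix which of the two it means.

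The missing fourth course in section 5 matters less. It touches the compliance denominator and the time between the last infusion and Visit 4.

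**Working it through.** The protocol gives no figure to reproduce here. The check is day arithmetic and a count of infusions.

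**1. End of cycle 3.** Ten consecutive days from day 121 end on 121 + 10 − 1 = day 130. That agrees with the cycle heading.

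**2. Gap to Visit 3.** 180 − 130 = 50 days under the heading; 0 days under the sentence on the last infusion.

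**3. Can the window close the gap?** Let each event move by *s* calendar days towards the other. The gap is then (180 − *s*) − (130 + *s*).
- *s* = 3: 177 − 133 = 44 days.
- *s* = 5 (assumption: three working days spanning a weekend): 175 − 135 = 40 days.

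**4. Can the make-up rule close it?** Suppose all ten infusions were missed and added at the end of a course that is already five days late: 130 + 5 + 10 = day 145. The earliest Visit 3 is day 175, so 30 days remain.

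**5. Can the sentence be met in another way?**
- Ten consecutive days ending on day 180 would be days 171 to 180. No section lists them.
- Holding one infusion back until day 180 breaks the consecutive-day requirement.
- Moving Visit 3 to day 130 shifts it by 50 days, far outside the window.

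**6. Number of courses.**

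| | Section 5 as narrated | Synopsis, 7.1.1, 11.1 |
|---|---|---|
| Courses | 3 | 4 |
| Planned infusions | 3 × 10 = 30 | 4 × 10 = 40 |
| 80% limit | 0.8 × 30 = 24 | 0.8 × 40 = 32 |
| Compliance with 30 infusions given | 30/30 = 100% | 30/40 = 75% |
| Last planned infusion to day 360 | 360 − 130 = 230 days | 360 − 250 = 110 days |

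A patient with 30 infusions is inside the per-protocol set under the first column and outside it under the second.

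**7. Length of the breaks.** Section 5 calls the treatment-free periods one month. Its own study days leave days 11 to 60 (61 − 10 − 1 = 50) and days 71 to 120 (121 − 70 − 1 = 50).

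**The case against.** The strongest reply is that one stray sentence stands against a consistent schedule. Days 121 to 130 appear in the synopsis, section 5, section 7.1.1 and the cycle 3 heading, and day 180 recurs throughout. The same paragraph calls cycle 3 the second cycle, and the cycle 4 paragraph repeats the slip, so leftover text is plausible. That may be so, but the protocol does not say it. Nor is day 180 labelled consistently elsewhere: section 13.7 calls it month 4 after stroke, while section 4.1 calls it 7 months. A reader is not entitled to discard the sentence on a guess.

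Several stronger readings are tempting and are not supported:

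- **Three courses against four as a flat contradiction.** Section 5 never says that there are only three. It stops narrating after the third, and three other places give the fourth with dates. The 30-infusion denominator arises only if that silence overrides them.
- **Sites mixing two schedules.** The synopsis names one study location. Sections 5 and 6.7.1 do speak of centres and sites in general terms, but nothing shows that patients would be treated under different readings.
- **Acute effect against lasting effect.** The protocol gives no interval between infusion and testing within the day, and says nothing about acute or lasting action of the drug. What follows is only that the quantity measured is undefined.
- **Bias between arms or inflated type I error.** Both arms follow the same schedule under blinding, so the problem is one of interpretation.

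The wording on one-month breaks is minor, because section 5 gives the exact days beside it.

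**Conclusion.** The concern holds for cycle 3 and Visit 3. Section 11.1 contradicts its own heading and the rest of the protocol by 50 days. At least 40 days remain after the full window is used on both sides, taking three working days as at most five calendar days, and 30 days remain even if a whole course of make-up infusions is added. Because this determines what the first confirmatory comparison measures, it is more than a clerical slip and needs correcting.

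The second part holds only as an omission. Section 5 leaves out the fourth course and describes its 50-day breaks loosely. The shift from 40 to 30 planned infusions, and from 32 to 24 at the 80% limit, is conditional on someone following section 5 alone.

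**What to change.** Reconcile the synopsis, section 5, section 7.1.1 and section 11.1 to one schedule that states the number of courses, the treatment-free gaps, and the timing of Visit 3 relative to the last cycle 3 infusion. The sponsor and the investigator must decide which version is intended; this review takes no position.

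Then state the resulting number of planned infusions as the compliance denominator in sections 11.2 and 13.14.

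At the blind review under section 13.15, derive for each patient the interval from the last infusion to each efficacy visit, so that any visit run under a different reading is identified before unblinding. Section 11.2 already requires the date and time of every administration in the CRF, so no new CRF item is needed.

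The cost is amendment wording, with the ethics committee opinion that section 16.4 requires, and a clarification letter to study staff. No procedure is added.
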